5.3.3. Concomitant Medications

Prior and concomitant medications will be coded using the World Health Organization (WHO) dictionary version WHODrug Global b3 September 2023 release. Concomitant medications will be summarized by ATC Classification, preferred name, and treatment group. Prior and concomitant medications will be presented in a data listing.

5.3.4. Other Safety Analyses

Descriptive summaries of vital signs and their respective change from Baseline values will be presented by time point and treatment group. The number and percentage of subjects with PCS vital signs occurring post-baseline will also be summarized by time point and treatment group. All abnormalities that occur post-baseline, regardless of Baseline status will be included. All vital signs will be listed with PCS vital signs flagged.

Table 3. Criteria For Potentially Clinically Significant Vital Signs

Vital Sign Parameter	Flag	Criteria
Systolic Blood Pressure	High	≥ 150 mmHg
(mmHg)	Low	≤ 80 mmHg
Diastolic Blood Pressure	High	≥100 mmHg
(mmHg)	Low	≤ 45 mmHg
Heart Rate (bpm)	High	> 115 bpm
	Low	< 45 bpm
Temperature (°C)	High	≥ 38 °C
	Low	< 35 °C

ECG parameters and their change from Baseline (using both Study Baseline and Treatment Phase 2 Baseline) will be summarized with descriptive statistics by time point and treatment group. ECG parameters will include heart rate, PR interval, RR interval, QRS interval, QT interval, and QTc interval corrected for heart rate using QTcB and QTcF. QTcF values will also be tabulated for their absolute values and tabulated relative to Baseline measurements in order to detect individual QTcF changes.

Additionally, the number and percentage of subjects with post-baseline QTcF interval > 450 - 480 milliseconds (msec), > 480 - 500 msec, or > 500 msec will be summarized, as will the number and percentage of subjects with QTcF interval increases from Baseline of > 30 - 60 msec or > 60 msec. For these summaries, worst-case assignments will be made to ensure subjects with such values are not counted more than once. For example, a subject with QTc interval > 500 msec will count once in the > 500 msec category and will not appear in the > 450 - 480 or > 480 - 500 msec categories. Similar conventions will be used for the > 30 - 60 and > 60 msec categories.

All ECG assessments and abnormalities in ECG waveform that are changes from Baseline readings will also be reported in a listing.

Final Version

Table 4. Potentially Clinically Significant Criteria for ECG

[figure not shown]
Variable	Units	PCS Criteria Low Values	PCS Criteria High Values	Change from Baseline or Observed Value
Heart Rate	beats/min	<45	>115	-
QTcF Interval	msec	-	>450 Males >470 Females	>30-60, > 60, > 450-480, > 480-500, > 500
QRS Interval	msec	-	>120	-
PR Interval	msec	-	>220	-

All physical examination results will be listed.

Extrapyramidal symptoms will be assessed by AIMS and BARS. Observed and change from baseline (both Study Baseline and Treatment Phase 2 Baseline) in AIMS and BARS will be summarized by treatment group and time point for Safety Set. Separate listings will be provided for AIMS and BARS for Safety Set.

Suicidal ideation will be assessed by C-SSRS. Observed and change from baseline (both Study Baseline and Treatment Phase 2 Baseline) in C-SSRS will be summarized by treatment group and time point for Safety Set. Separate listings will be provided for C-SSRS for Safety Set.

Tuberculosis, FSH, Pregnancy Test, Drug Screen and Alcohol Breath Test, SARS-CoV2 Test, and Serology Test will be listed for the Safety Set.

Final Version

6. **PROTOCOL VIOLATIONS**

Possible protocol deviations will be identified and displayed in a data listing and sorted by Treatment-Phase, subject, and study day (where applicable). The following deviations may be identified as protocol deviations from the database:

- Missing ECG or PK assessments
- Violations of inclusion/exclusion criteria
- Non-compliance with roluperidone and/or olanzapine

7. CHANGES IN THE PLANNED ANALYSES

No deviations in the conduct of the study or the planned analysis are anticipated. Should any deviations from the analyses specified in the authorized statistical analysis plan arise, such deviations will be documented in the final clinical study report (CSR).

Final Version

8. **PROGRAMMING CONVENTIONS**

- Page orientation, margins, and fonts: Summary tables, listings, and figures will appear in landscape orientation. There should be a minimum of a 1.0" boundary on the left and right edges. The top and bottom margins are 1.0" for tables and listings but may vary for figures. The output should be printed in Courier New with point size of 8.
- Identification of analysis population: Every summary table and figure should clearly specify the analysis population being summarized. Listings will be prepared for all subjects.
- Group headers: In the summary tables, the group headers will identify the summary group and the sample size for the indicated analysis population. Of note, the header's sample size does not necessarily equal the number of subjects actually summarized within any given summary module; some subjects in the analysis population may have missing values and thus may not be summarized.
- Suppression of percentages corresponding to null categories: When count data are presented as category frequencies and corresponding percentages, the percentage should be suppressed when the count is zero in order to draw attention to the non-zero counts.
- Presentation of sample sizes: Summary modules should indicate, in one way or another, the number of subjects contributing to the summary statistics presented in any given summary module. As mentioned above, this may be less than the number of subjects in the analysis population due to missing data.
 - In the quantitative modules describing continuous variables (and thus presenting sample size, means, and standard deviations), the sample size should be the number of non-missing observations. The number of missing observations, if any, will be noted.
 - For categorical variables that are presented in frequency tables, the module should present the total count in addition to the count in each category. Percentages should be calculated using this total as the denominator, and the percentage corresponding to the sum itself (that is, 100%) should be presented so as to indicate clearly to a reviewer the method of calculation. The number of missing observations, if any, will be noted.
- Sorting: Listings will be sorted by treatment group, subject number, and date, if applicable. If a listing is sorted in a different manner, a footnote will indicate as such.
- General formatting rules: Rounding for all variables will occur only as the last step, immediately prior to presentation in listings, tables, and figures. No intermediate rounding will be performed on derived variables. The standard rounding practice of rounding numbers ending in 0-4 down and numbers ending in 5-9 up will be employed.
- The presentation of numerical values will adhere to the following guidelines:
 - Raw measurements will be reported to the number of significant digits as captured electronically or on the CRFs.
 - Standard deviations will be reported to one decimal place beyond the number of decimal places the original parameter is presented.

Final Version

- Means and medians will be reported to the same number of significant digits as the parameter.
- ◆ Calculated percentages will be reported with no decimals.
- Dates will be formatted as DDMMMYYYY. Partial dates will be presented on data listings as recorded on CRFs.
 - Time will be presented according to the 24-hour clock (HH:MM).

Statistical Analysis Plan Final Version

9. **PROPOSED TABLES, LISTINGS, AND FIGURES**

Summary Tables

Accountability	and Baseline Characteristics
14.1.1.1	Subject Disposition, Full Set
14.1.1.2	Analysis Sets, Full Set
14.1.2	Demographics and Baseline Characteristics, Safety Set
14.1.3	Medical and Psychiatric History, Safety Set
14.1.4	Concomitant Medications, Safety Set

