Additional information about roluperidone is provided in the Investigator's Brochure.

Olanzapine is among the most frequently used drugs to treat acute exacerbation of psychosis in schizophrenia. Once psychosis ameliorates or stabilizes, olanzapine is used as maintenance

treatment to reduce the risk of recurrence of psychosis. Olanzapine has affinities for dopaminergic, cholinergic, serotonergic, and histaminergic receptors. As such it can produce extrapyramidal, parkinsonian effects, sedation, constipation, blurry vision, and weight gain.

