2. OBJECTIVES AND ENDPOINTS

Objectives	Endpoints						
To evaluate the pharmacodynamics (PD), including safety and tolerability of the coadministration of roluperidone 64 mg and olanzapine	Safety assessments, including adverse events (AEs), clinical laboratory, electrocardiogram (ECG), vital signs, extrapyramidal symptoms (assessed by Abnormal Involuntary Movement Scale [AIMS] and Barnes Akathisia Rating Scale [BARS]), and suicidal ideation (assessed by the Columbia Suicide Severity Rating Scale [C-SSRS])						
To evaluate the effect of the coadministration of roluperidone and olanzapine on the pharmacokinetics (PK) of roluperidone in subjects with moderate to severe negative symptoms of schizophrenia	 The plasma pharmacokinetic parameters of roluperidone and its metabolite, BFB-520, following single dose and at steady state (C_{max}, T_{max}, AUC₀₋₂₄, AUC_∞) Plasma pharmacokinetic parameters of roluperidone and BFB-520 when administered concomitantly with olanzapine The plasma pharmacokinetic parameters of olanzapine administered concomitantly with roluperidone compared to its pharmacokinetic profile based on monotherapy administration from published literature 						
	Clinical Global Impression- Severity Rating (CGI-S)						

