If a significant prolongation in QT is observed, a PK sample should be obtained.

Physical Examination

Physical examinations as well as anthropomorphic measurements (height and weight) will be performed at the times specified in the TIME AND EVENTS SCHEDULE.

Any abnormalities present at Baseline, or subsequent changes, will be documented in the

stable endpoint.

appropriate sections of the CRF. Any clinically significant abnormalities persisting at the end of the study will be followed by the investigator until resolution or until reaching a clinically

AIMS is rating scale that was designed in the 1970s to measure TD will be performed at the times specified in the TIME AND EVENTS SCHEDULE. TD is a disorder that sometimes develops as a side effect of long-term treatment with neuroleptic (antipsychotic) medications. The AIMS test is used not only to detect TD but also to follow the severity of a patient's TD over time. The AIMS test is usually given every 3 to 6 months to monitor the patient for the development of TD. For most patients, TD develops 3 months after the initiation of neuroleptic therapy; in elderly patients, however, TD can develop after as little as one month. The entire test can be completed in about 10 minutes. The AIMS test has a total of 12 items rating involuntary movements of various areas of the patient's body. These items are rated on a 5-point scale of severity from 0–4. The scale is rated from 0 = none, 1 = minimal, 2 = mild, 3 = moderate, 4 = severe. Two of the 12 items refer to dental care. The patient must be calm and sitting in a firm chair that doesn't have arms, and the patient cannot have anything in his or her mouth. The clinician asks the patient about the condition of his or her teeth and dentures, or if he or she is having any pain or discomfort from dentures.

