ATTACHMENT 5: ABNORMAL INVOLUNTARY MOVEMENT SCALE (AIMS)

Public Health Service	NAME:	
Alcohol, Drug Abuse, and Mental Health Administration	DATE:	
National Institute of Mental Health	Prescribing Practitioner:	
	CODE:	0 = None
		1 = Minimal, may be extreme normal

 INSTRUCTIONS:
 2 = Mild

 Complete Examination Procedure (attachment d.)
 3 = Moderate

 before making ratings
 4 = Severe

before making rating	S	4 = Severe		
	TNGS: Rate highest severity observed. Rate ir upon activation one less than those observed	RATER	RATER	RATER
spontaneously. Circle	e movement as well as code number that applies	Date	Date	Date
Facial and	1. Muscles of Facial Expression	0 1 2 3 4	0 1 2 3 4	0 1 2 3 4
Oral Movements	e.g., movements of forehead, eyebrows, periorbital area, cheeks, including frowning, blinking, smiling, grimacing			
	2. Lips and Perioral Area	0 1 2 3 4	0 1 2 3 4	0 1 2 3 4
	e.g., puckering, pouting, smacking			
	Jaw e.g., biting, clenching, chewing, mouth opening, lateral movement	0 1 2 3 4	0 1 2 3 4	0 1 2 3 4
	4. Tongue Rate only increases in movement both in and out of mouth. NOT inability to sustain movement. Darting in and out of mouth.	0 1 2 3 4	0 1 2 3 4	0 1 2 3 4
Extremity Movements	5. Upper (arms, wrists, hands, fingers) Include choreic movements (i.e., rapid, objectively purposeless, irregular, spontaneous) athetoid movements (i.e., slow, irregular, complex, serpentine). DO NOT INCLUDE TREMOR (i.e., repetitive, regular, rhythmic)	0 1 2 3 4	0 1 2 3 4	0 1 2 3 4
	6. Lower (legs, knees, ankles, toes) e.g., lateral knee movement, foot tapping, heel dropping, foot squirming, inversion and eversion of foot	0 1 2 3 4	0 1 2 3 4	0 1 2 3 4
Trunk Movements	7. Neck, shoulders, hips e.g., rocking, twisting, squirming, pelvic gyrations	0 1 2 3 4	0 1 2 3 4	0 1 2 3 4
Global Judgments	8. Severity of abnormal movements overall	0 1 2 3 4	0 1 2 3 4	0 1 2 3 4
	9. Incapacitation due to abnormal movements	0 1 2 3 4	0 1 2 3 4	0 1 2 3 4
	10. Patient's awareness of abnormal movements. Rate only patient's report No awareness 0 Aware, no distress 1 Aware, mild distress 2 Aware, moderate distress 3 Aware, severe distress 4	0 1 2 3 4	0 1 2 3	0 1 2 3
Dental Status	11. Current problems with teeth and/or dentures?	No Yes	No Yes	No Yes
	12. Are dentures usually worn?	No Yes	No Yes	No Yes
	13. Edentia?	No Yes	No Yes	No Yes
	14. Do movements disappear in sleep?	No Yes	No Yes	No Yes

Final: 9/2000

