2. OBJECTIVES

Primary Objective:

To evaluate the pharmacodynamics (PD), including safety and tolerability of the coadministration of roluperidone 64 mg and olanzapine.

- Adverse events (AEs)
- Laboratory evaluations
- Physical examination (including weight, baseline height and BMI)
- Vital signs (including blood pressure, heart rate, respiratory rate, pulse, temperature)
- 12-Lead electrocardiograms (ECGs)
- Extrapyramidal symptoms (assessed by Abnormal Involuntary Movement Scale (AIMS) and Barnes Akathisia Rating Scale (BARS))
- Suicidal ideation (assessed by the Columbia Suicide Severity Rating Scale (C-SSRS))

Secondary Objective:

To evaluate the effect of the coadministration of roluperidone and olanzapine on the pharmacokinetics (PK) of roluperidone in subjects with moderate to severe negative symptoms of schizophrenia. The secondary endpoint, PK, will include the following parameters:

- PK parameters of roluperidone and its metabolite, BFB-520, following single dose and at steady state.
- PK parameters of roluperidone and BFB-520 when administered concomitantly with olanzapine.
- PK parameters of olanzapine administered concomitantly with roluperidone compared to its pharmacokinetic profile based on monotherapy administration from published literature.

PK parameters are included but are not limited to the variables given below:

- C_{max}: observed maximum plasma concentration (ng/mL).
- t_{max} : time to reach the observed maximum plasma concentration (h).
- AUC₀₋₂₄: area under the plasma concentration-time curve from time 0 to concentration C₂₄ (ng.h/mL) at the 24-hour time point.
- AUC_{∞} : area under the plasma concentration-time curve from time 0 to infinite time, calculated according to the following equation $AUC_{\infty} = AUC_{last} + C_{last} / \lambda z$ (ng.h/mL), where C_{last} is the last measurable plasma concentration and λz is the terminal elimination rate constant.

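### The extrapyramidal endpoint uses only a dyskinesia scale (AIMS) and an akathisia scale (BARS), so a clean Table 14.3.8 cannot by itself support absence of extrapyramidal symptoms

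*SAP*

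**What the plan says.** Extrapyramidal symptoms are one component of the primary objective on safety and pharmacodynamics. Protocol Section 2 and SAP Section 2 both name AIMS and BARS as the means of assessing them. SAP Section 5.3.4 repeats this: "Extrapyramidal symptoms will be assessed by AIMS and BARS". It then plans descriptive summaries of observed values and changes from baseline. The output is Table 14.3.8, which carries extrapyramidal symptoms in its title.

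Protocol Section 6.5 describes the two instruments. On the first it says: "AIMS is rating scale that was designed in the 1970s to measure TD". It describes BARS as an assessment of akathisia. The AIMS form in Attachment 5 carries the instruction "DO NOT INCLUDE TREMOR" in item 5, upper extremities.

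Of olanzapine, Protocol Section 1.2 says "it can produce extrapyramidal, parkinsonian effects, sedation, constipation, blurry vision, and weight gain". Section 12.1 lists EPS among its well-known adverse effects.

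On the content of AIMS, Section 6.5 says "The AIMS test has a total of 12 items rating involuntary movements", and counts two of the 12 as dental. The form in Attachment 5 has 14 items. SAP Section 5.3.4 does not say which AIMS score is summarised.

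**The concern.** Dyskinesia and akathisia are two kinds of extrapyramidal symptom. Parkinsonism is a third, and the protocol itself attributes it to olanzapine. Section 1.2 also says that roluperidone alone does not induce it. A shift in parkinsonian signs between Treatment Phase 1 and Treatment Phase 2 is therefore a natural thing to look for in this design, yet the output named for extrapyramidal symptoms has no item for rigidity or slowness.

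The protocol says that the results are meant to guide clinicians who may prescribe the two drugs together. A flat Table 14.3.8 under its present title invites the reading that the combination produced no extrapyramidal symptoms, when it would show only no change in dyskinesia or akathisia ratings.

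**Working it through.** The documents give no rate, margin or power for extrapyramidal symptoms, and the analysis is descriptive, so there is no figure to reproduce. The check sets the forms against the label.

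**1. Coverage of the two scales**

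| Sign | AIMS, Attachment 5 | BARS, Attachment 6 |
|---|---|---|
| Abnormal movements of face, mouth, limbs, trunk | Items 1–7 | Not rated |
| Akathisia | No dedicated item | All four ratings |
| Tremor | Left out of item 5 (upper limbs); no item of its own | Not rated |
| Rigidity | No item | Not rated |
| Slowness | No item | Not rated |

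**2. Other routes by which parkinsonism could be seen**

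- Adverse events. Section 6.5 has subjects report them, and the synopsis adds investigator observation. SAP Section 5.3.1 tabulates them by system organ class and preferred term, by treatment group. It defines no extrapyramidal grouping, and the special-interest list is confined to syncope, sudden or cardiac death, QT, ECG-wave and ventricular-rhythm events.
- Physical examination. It is scheduled at Screening, Day -1, Day 17 and end of study. SAP Section 5.3.4 lists the results without summarising them.

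Neither route is a structured rating of parkinsonism, and neither feeds Table 14.3.8.

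**3. What the preferred-term tables leave open**

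Rows for related terms cannot be added to give subjects. As a hypothetical example, one subject in a tremor row and one in a rigidity row, among 12, could be one subject (1/12 = 8.3%) or two (2/12 = 16.7%). A count of subjects with any term in the group settles this.

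**4. How much a clean result could show at this size**

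The plan is for about 18 subjects dosed and at least 12 completing the combination. With zero events in n subjects, the one-sided 95% upper limit is 1 − 0.05^(1/n).

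- n = 12: 1 − 0.05^(1/12) = 22.1%
- n = 18: 1 − 0.05^(1/18) = 15.3%

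These limits assume that every case is detected. To show the effect of detection, assume a true rate of parkinsonism of 10% to 20%; this range is not in the documents. The chance of at least one detected case in 12 is 1 − (1 − rate × detection)^12:

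- full detection: 71.8% to 93.1%
- half detected: 46.0% to 71.8%
- a quarter detected: 26.2% to 46.0%
- signs that neither scale rates: 0% from those scales

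**5. AIMS score (secondary)**

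The form has seven movement items and three global or awareness items, each rated 0–4, and four yes/no items.

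- Items 1–7: 7 × 4 = 28, range 0–28
- Items 1–10: 10 × 4 = 40, range 0–40

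Both readings are open under SAP Section 5.3.4. If items 1–10 were summed, a movement already scored in items 1–7 could be counted again in the global items. As an upper illustration, one movement scored 2 with each of the three global items also scored 2 gives 2 + 3 × 2 = 8 instead of 2.

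**The case against.** The best defence is that the primary objective rests on the whole safety dataset. All adverse events are recorded from consent onwards and tabulated by preferred term and treatment group, examinations are done, and stopping criterion 12 already asks investigators to tell extrapyramidal tremor from other tremor. That stands. A reader might infer that nothing in the trial could reveal parkinsonism, and the documents do not support this. The gap lies in the output labelled extrapyramidal symptoms.

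Other stronger readings also fail.

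- *The protocol expects parkinsonism.* Section 1.2 says only that olanzapine can produce it.
- *AIMS is uninformative because olanzapine is given for 10 days.* Section 6.5 does say "For most patients, TD develops 3 months after the initiation of neuroleptic therapy", but that clock starts with first neuroleptic treatment. Subjects have had the diagnosis for at least a year and those on psychotropics are washed out, so many have probably been treated before. Section 6.5 also gives AIMS the role of following existing dyskinesia.
- *AIMS excludes tremor throughout.* The instruction is printed in item 5 only.
- *The AIMS range could be 0–48.* That needs 12 items rated 0–4, whereas the dental items on the attached form are yes/no.
- *The sponsor will report a clean table as absence of extrapyramidal symptoms.* No passage says so; the title merely invites it.

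Some schedule rows and attachments are blacked out. The two unlabelled rows have no Day 8 assessment, unlike AIMS and BARS, and every readable definition of the endpoint names only those two scales.

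It can also be said that relabelling and regrouping add no new measurement. That is true: the change limits what a clean table can claim and adds one subject-level figure, but it does not create a parkinsonism rating.

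**Conclusion.** The point holds in a limited form. Table 14.3.8 measures dyskinesia and akathisia, and its label covers more than that. A clean table cannot by itself support absence of extrapyramidal symptoms, because rigidity and slowness are not rated and upper-limb tremor is left out. The evidence on those signs lies in separate adverse-event rows and in examination listings.

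This rests on the forms as attached and on the readable text. It needs no assumption about how often parkinsonism occurs; the detection figures are illustrations only. The practical weight is moderate, since this is a small descriptive study and the gap is in labelling and grouping. The AIMS scoring point is a missing detail, which matters because two programmers could follow the SAP and produce tables on different scales.

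**What to change.** 1. In Protocol Section 2, SAP Sections 2 and 5.3.4, and the title of Table 14.3.8, label the endpoint as dyskinesia (AIMS) and akathisia (BARS).
2. In SAP Section 5.3.1, predefine a group of extrapyramidal preferred terms, for example tremor, rigidity, bradykinesia, parkinsonism, akathisia and dyskinesia. Tabulate the number of subjects with any such treatment-emergent event, by treatment group.
3. In SAP Section 5.3.4, state the AIMS score. A workable choice is the sum of items 1–7 (0–28), with items 8–10 reported separately. The documents do not dictate this choice, but one has to be fixed before the tables are produced.
4. Align the AIMS description in Protocol Section 6.5 with the 14-item form in Attachment 5.

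The cost is wording in two documents and one additional adverse-event table. No new assessment is needed. The downside is a narrower stated endpoint.

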- 4 *Marked akathisia*. Subjective experience of restlessness includes a compulsive desire to walk or pace. However, the patient is able to remain seated for at least five minutes. The condition is obviously distressing.
- **Severe akathisia.** The patient reports a strong compulsion to pace up and down most of the time. Unable to sit or lie down for more than a few minutes. Constant restlessness which is associated with intense distress and insomnia.

Scoring the Barnes Akathisia Rating Scale

The Barnes Akathisia Rating Scale is scored as follows:

Objective Akathisia, Subjective Awareness of Restlessness and Subjective Distress Related to Restlessness are rated on a 4-point scale from 0-3 and are summed yielding a total score ranging from 0 to 9.

The Global Clinical Assessment of Akathisia uses a 5-point scale ranging from 0-4.

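### The SAP rounds means and medians by significant digits but SDs by decimal places, so on one-digit scales any mean of 1 or more prints as a whole point, less precisely than its own SD

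*SAP*

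**What the plan says.** The number-format rules are in SAP section 8 (Programming Conventions).

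- Raw values: "Raw measurements will be reported to the number of significant digits as captured electronically or on the CRFs".
- SDs: "Standard deviations will be reported to one decimal place beyond the number of decimal places the original parameter is presented".
- Means and medians: "Means and medians will be reported to the same number of significant digits as the parameter".
- Direction of rounding: "The standard rounding practice of rounding numbers ending in 0-4 down and numbers ending in 5-9 up will be employed".
- Timing: "Rounding for all variables will occur only as the last step, immediately prior to presentation in listings, tables, and figures".

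The scales most affected are scored in single digits. For BARS, three items rated 0 to 3 "are summed yielding a total score ranging from 0 to 9" (protocol Attachment 6). For AIMS, protocol section 6.5 says "These items are rated on a 5-point scale of severity from 0–4". CGI-S runs from 1 to 7 in its protocol attachment, with 0 for not assessed.

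SAP section 5.3.4 plans that observed values and changes from both baselines "in AIMS and BARS will be summarized by treatment group and time point for Safety Set". For CGI-S, the visible SAP text gives a table by treatment phase (14.2.1.3) and a listing.

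**The concern.** Two adjacent rules use different units. A significant-digit rule ties the precision of a mean to how many digits the raw score has, so a one-digit score gets a one-digit mean. The SD rule gives the same score one decimal. A mean of 1 or more is then shown more coarsely than the spread around it.

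AIMS and BARS are listed under the primary objective in SAP section 2, and no model or test is planned for them. Whatever Table 14.3.8 prints is the group-level result. In 12 to 18 subjects measured over short intervals (Days 7, 8 and 17), a reader would look for shifts of a fraction of a point, and the format can hide such shifts or exaggerate them.

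**Working it through.** The plan gives no figure of its own to reproduce here. The check applies the stated rule to the means that can occur.

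**Inputs.** One-digit integer scores (protocol Attachment 6, section 6.5 and the CGI-S attachment); half-up rounding (SAP section 8); n = 12 completers and n = 18 enrolled (SAP section 3.2).

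**Rule.** A mean is (sum of scores)/n. To one significant digit, a value from 1 up to 9 is rounded to the nearest 1, a value from 0.1 to below 1 to the nearest 0.1, and a value from 0.01 to below 0.1 to the nearest 0.01. The raw scores have no decimals, so the SD is rounded to the nearest 0.1. For a mean of 1 or more, the largest rounding error is therefore 0.5 point, against 0.05 for its SD.

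**Observed means of 1 or more**

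| n | Sum of scores | Mean | Prints as |
|---|---|---|---|
| 12 | 41 | 3.42 | 3 |
| 12 | 42 | 3.50 | 4 |
| 12 | 53 | 4.42 | 4 |
| 18 | 63 | 3.50 | 4 |
| 18 | 80 | 4.44 | 4 |

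With n = 12, the sum can rise by 53 − 42 = 11 points (eleven subjects each one point worse) and the printed mean stays at 4. With n = 18, the sum can rise by 80 − 63 = 17 points with the same result. In the other direction, one subject moving one point (41 to 42) changes the printed mean from 3 to 4. A median of 3.5, possible with an even n, prints as 4.

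**Mean changes of 1 or more.** For n = 12, 12/12 = 1.00 to 17/12 = 1.42 all print as 1. For n = 18, 18/18 = 1.00 to 26/18 = 1.44 all print as 1. From 1.50 to 2.00 every value prints as 2.

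**Mean changes below 1.** The result depends on the reading.

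| Mean change | One significant digit (literal) | No decimal places (alternative) |
|---|---|---|
| 1/12 = 0.083 | 0.08 | 0 |
| 3/12 = 0.25 | 0.3 | 0 |
| 0.42 | 0.4 | 0 |
| 6/12 = 0.50 | 0.5 | 1 |
| 11/12 = 0.92 | 0.9 | 1 |

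The literal reading puts 0.08, 0.4 and 1 in one column with three different precisions.

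**With means at one decimal place beyond the raw score.** 3.50 and 4.42 print as 3.5 and 4.4, and 1.42 prints as 1.4. The smallest nonzero mean change for these n, 1/18 = 0.056, prints as 0.1, so none prints as 0.0.

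**The case against.** The strongest reply is that this is format, not analysis. Rounding is the last step, so no estimate or interval is computed from rounded values. SAP section 5 also reports SD, minimum and maximum, and AIMS, BARS and CGI-S are all listed by subject. That stands, and it keeps the point minor. It does not remove it: a reader should not have to rebuild a group mean from listings when that mean is the planned result.

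A reader might infer something stronger: that any shift below half a point prints as 0, so the tables would suggest no change. The documents do not support this. Leading zeros are not significant digits, so 0.42 and 0.44 both print as 0.4, and a median change of 0.5 prints as 0.5. Zeros appear only if significant digits is taken to mean decimal places. The neighbouring SD rule makes that slip plausible, but the SAP does not say it. Under the literal reading, the AIMS and BARS change rows would also show a shift that the observed means conceal, provided the mean change is below 1.

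Two limits on scope also stand. The SAP does not say whether AIMS is summarized by item or as a total. A total treated as a two-digit score would print 1.42 as 1.4, without whole-point rounding at that size. And the visible SAP text plans no CGI-S change from baseline. Part of that text may be redacted, so its absence is not counted as a fault.

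**Conclusion.** The point holds as a minor reporting defect. On BARS total, single AIMS items and CGI-S, every mean, median or mean change of 1 or more prints as a whole point beside an SD with one decimal. Observed means almost a full point apart (3.50 and 4.42 with n = 12; 3.50 and 4.44 with n = 18) print the same. For changes below 1 the rule is ambiguous, and it would be wrong to say that they vanish.

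This assumes that the scores are summarized as continuous variables with means, that a one-digit score counts as one significant digit, and that group sizes are near the planned 12 to 18. No inferential result is affected.

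**What to change.** Replace the two sentences in SAP section 8 on means, medians and SDs with: *Means and medians, and their changes from baseline, will be reported to one decimal place more than the raw data, and standard deviations to two more.* This puts both rules in the same unit and settles the reading for changes below 1. It would also help to state in section 5.3.4 whether AIMS is summarized by item or as a total.

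The cost is a one-sentence SAP edit and a change of output format. No new data or analysis is needed.
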